The aims of this application are to gain information in children with NF1 about possible clinical benefit of anti-oxidant treatment and to develop and evaluate quantitative brain-based and blood biomarkers relating to presence of NF1, symptom severity, and response to antioxidant therapy. Clinically, 50% of children with NF1 are underperforming or failing at school [1]. This frequently leads to decreased educational attainment and fewer opportunities as adults. An important first step was our preliminary work using the PANESS scale and Transcranial Magnetic Stimulation (TMS)-evoked Short Interval Cortical Inhibition (rSICI) in children with NF1. We propose to develop and extend our understanding of NF1-related motor and learning behavior in response to antioxidant therapy with NAC. The purpose of the present study is to 1) evaluate tolerability, safety, and clinical benefit of NAC in this double-blind placebo controlled study; 2) to evaluate motor function (PANESS) and physiology (TMS) biomarkers at baseline and after treatment; and 3) to quantify metabolomics profiles at baseline and after treatment. We propose to study 20 children with NF1, ages 8-16 years, at baseline and after completion of 8 weeks of treatment with NAC.

NAC therapy, if successful, is expected improve these parameters. Our trial endpoints are: Does behavior improve? Does motor function improve? Are there TMS biomarkers that reflect the presence of NF1 and the response to NAC treatment? Are there metabolomics measures that reflect the presence of NF1 and the response to treatment? We hypothesize that we can identify predictive measures as a foundation for an application for funding for a larger, more definitive, placebo-controlled trial involving biomarkers and clinical outcomes. We believe this work has the potential to lay groundwork for future use of relevant biomarkers for treatment and outcomes research for NF1 as well as other biologically similar conditions, collectively designated the "RASopathies" (due to involvement of the RAS family of proteins) and ultimately to guide development of more effective treatments based on disease pathophysiology.

SPECIFIC AIMS

This study involves the following aims:

Specific Aim 1: Primary Outcome of Study

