In children and adolescents with NF1, to characterize the behavioral and motor effects of 8 weeks of N-acetylcysteine (NAC) treatment in a cohort of 20 children and adolescents with NF1. We will evaluate tolerability, safety, and clinical benefit of NAC in this double-blind crossover placebo controlled study. Aim 1.1: Characterize effects of NAC treatment on motor function in kids with NF1 using the Physical and Neurological Examination for Subtle Signs (PANESS). This is a validated scale that consistently demonstrates significant impairments in children with ADHD, and which our preliminary data suggest may demonstrate more extreme problems in children with NF1 than age-matched healthy controls (unpublished data from CCHMC). We hypothesize that motor function scores rated with the PANESS scale will improve

Version 9.0 MAR2020 Page **3** of **24**

after treatment with NAC. **Aim 1.2**: Characterize effects of NAC treatment on ADHD symptoms in children with NF1. We hypothesize that ADHD attention and hyperactive/impulsive symptoms, rated with the DuPaul DSM-5 based clinical rating scales, will improve after treatment with NAC.

Specific Aim 2: Experimental aim # 1

In the same cohort, we will identify potential novel biomarkers of neurodevelopmental burden in NF1. Aim 2.1: Describe the function and physiology of the motor system using Transcranial Magnetic Stimulation (TMS) as a possible disease biomarker of NF1. Preliminary measures in our NF1 population also show abnormalities similar to established findings in ADHD. We hypothesize that children with NF1 will have significantly less motor cortex inhibition using TMS measurements, and these measures will improve ("normalize") upon NAC treatment. We will compare to our internal age-matched healthy controls at Cincinnati Children's. Aim 2.2: We propose to evaluate autotaxin as a candidate biomarker of oligodendrocyte dysfunction in NF1 participants. Preliminary data from our biomarker discovery analysis of serum samples from healthy controls and NF1 patients showed lysophosphatidylcholine (LPC) depletion compared to healthy age/sex matched controls. In gene expression analysis autotaxin was elevated 4 times in neurofibroma Schwann cells compared to normal nerve Schwann cells. We will collect serum and plasma from participants to assess autotaxin/LPC axis prior and post-NAC therapy. We hypothesize that autotaxin axis abnormalities will be a biomarker of response to antioxidant therapy in our NF1 population.

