
Specific Aim 3: Experimental aim # 2

In the same cohort, to evaluate metabolomics profiles as a possible disease biomarker that is affected by NF1 and by treatment with NAC as per Aim 1. Hypothesis 4: We hypothesize that specific profiles will predict clinical response to antioxidant therapy compared to age-matched healthy control (unpublished data from CCHMC).

BACKGROUND:

Neurofibromatosis (NF1) – overview

Neurofibromatosis (NF1) is an autosomal dominant condition affecting many organs, resulting from mutations in the neurofibromin gene [2]. Characteristically, individuals with this condition have cutaneous manifestations, most prominently hyperpigmented macules termed "café-au-lait" spots. The neurofibromin gene functions in part as a tumor suppressor, and persons with NF1 are susceptible to malignant and benign tumors in multiple organs. What is less well studied is that individuals with NF1 commonly suffer from difficulties with behavioral and emotional regulation including ADHD symptoms, learning disabilities, and developmental delays in motor function [3]. These cause substantial morbidity in adulthood.

NF1 – challenges evaluating behavioral, emotional, and cognitive symptoms

Clinically, 50% of children with NF1 are underperforming or failing in school [1]. This frequently leads to decreased educational attainment and fewer opportunities as adults. The high prevalence of behavioral, emotional, and cognitive problems in persons with NF1 suggests that neurofibromin may play a role in structure and/or healthy, efficient function of the brain. Clarifying this is challenging because most likely behavioral, cognitive, and motor impairments in NF1 result, as in other genetic conditions, from multiple complex factors including environmental factors and genetic loading distinct from the major effect of mutations in neurofibromin [4]. Moreover, cognitive and behavioral symptoms are difficult to quantify. Rating scales capture impressions of parents and teachers in the important domains of home and school, but they are subjective ratings, not brain-based measures [5]. Moreover, if treatments during a clinical trial are beneficial, there may be biological changes that precede clinical ones. Measuring these changes may be important for validating treatment mechanisms and effects.

NF1 – neurobiological basis for behavioral, emotional, and cognitive symptoms and role for physiological biomarkers

Version 9.0 MAR2020 Page **4** of **24**

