METABOLOMICS DATA: untargeted global metabolomics profiling is a non-invasive technique that can help identify novel biomarkers that correlate with clinical disease and response in the setting of NF1. We have successfully performed untargeted metabolomics experiments using serum from healthy controls (n=12) and NF1 patients (n=18) collected from the NF1 center in our mass spectrometry laboratory. Patients with NF1 showed a distinct metabolomics signature compared to healthy age/sex match controls (Figure 3A). This preliminary data strongly supports our hypothesis that RAS-MAPK disorders can lead to detectable biochemical abnormalities. A clinical database with patient characteristics already exists at our center. We have input plexiform neurofibroma (PNF) growth to correlate with metabolomics data (Figure 3B). This technology will allow potential identification of candidate biomarkers that could correlate with different disease complications including behavioral abnormalities. We plan to collect samples from NAC treated individuals to identify compounds that mark response to therapy, and could serve as response biomarkers in a larger Phase II trial.

[figure not shown]

Figure 3. Neurofibromatosis type 1 metabolomics pattern is different from healthy controls. **A.** Heatmap was based on 203 compounds out of 5,206 statistically significant compounds (p<0.005, fold change >2). Selected compounds includes diacylglycerol, lysophospholipids, ceramides species and other compounds. Blue indicates low abundance and Red increased abundance.

B. A principal component sub-analysis of these samples suggests a different biochemical profile and 10 candidate biomarkers in the NF1 patients who have progressive plexiform neurofibromas (PNFs) versus NF1 patients without PNFs.

- **Figure 4.** Lysophosphatidylcholine (LPC) species are depleted in serum from NF1 patients. **A.** Volcano plot for biomarker discovery (p<0.005, fold change >2) shows low abundance of LPC18:0
- fold change >2) shows low abundance of LPC18:0 and PCo18:1 in NF1 patients versus healthy controls.
- **B**. Targeted mass spectrometry analysis of LPC species confirmed low LPC18:0 in NF1 patients (NF1^a) compared to controls (p<0.005). Replication cohort showed similar differences (NF1^b). **C**. Heatmap based on LPC species (p<0.005, fold change >2). All LPC species were low in the NF1 patient cohorts versus healthy. Blue indicates low abundance and Red increased abundance.

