Treatment Observation Period:

Phase I:

Study initiation will consist of motor PANESS and TMS measures (AIMS 1 and 2) and blood will be drawn for metabolomics profiles (AIM 3). Subjects will then return to the outpatient RASopathies clinic where they will be assigned to one of two treatment arms (NAC drug or placebo) of this study. Each subject will receive drug or placebo (visits 1 and 3) without feedback regarding treatment arm assignment to [name] until the end of the study. At each of these outpatient visits (visits 1 and 3) subjects will be assessed for vital signs, adverse events, pill counts and concomitant meds, and for motor/learning behaviors severity and improvement. At the final phase I and final study visits (visits 2 and 4, respectively), treatment outcomes will be rated by an independent rater as well as by the study physician ([name], or qualified designee) for motor/behavior improvement. A repeat longitudinal TMS study will occur at weeks 8 and 18 (at the end of phase I and phase II, respectively) while on a stable treatment dose of NAC or placebo (visits 2 and 4) by [name] within 8-10 hours following AM dosing. At end of the final phase I study visit (visit 2), subjects will undergo an 'interphase' for 1 week during which they will abstain from medication (drug or placebo). After interphase, subjects will enter phase two of this cross-over double-blind placebo controlled study and commence the alternative treatment arm.

Phase II:

In phase two, subjects will cross over to the opposite treatment arm (NAC drug or placebo) than they were assigned during phase one. All other details outlined in phase I will remain unchanged.

After both phases of the treatment observation period are complete, there will be a debriefing interview, in which children and their families will review both their performance during the trial and tolerability data (visit 5). A plan for follow-up care will be created by [name], or qualified designee, with referral for follow-up treatment. If needed, subjects will be given transition medication (atomoxetine or otherwise depending on effectiveness of study drug) until subject can establish appropriate care with a clinician.

Version 9.0 MAR2020 Page **9** of **24**

Emergency Study Extension

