SICI inhibition is measured in resting muscle with a paired-pulse paradigm using paired vs. single pulse conditions [26]. The first condition is a single test pulse, delivered at an intensity that consistently produces a 500-1500 mV MEP. In the second condition, a subthreshold stimulus (60% of RMT) is followed after by a test pulse. Twenty trials are performed for the single-pulse condition, and 20 each for the other interstimulus intervals 3 ms, 10 ms. Relative to the single pulse response, the 3 ms interval is inhibitory (SICI) and the 10 ms interval is excitatory (intracortical facilitation). The order of the intervals is varied randomly, and the interval between trials varies randomly by <20% around a mean of 6 seconds. SICI is expressed as a ratio of the mean MEP amplitude after the conditioned pulses divided by the mean MEP amplitude after the single pulses. A detailed review of systems will be obtained before and after TMS, and participants will be provided the number of the investigator and study coordinator to call if there are concerns about possible side effects after the laboratory visit.

A complementary functional neuroimaging technique is Magnetoencephalography (MEG). MEG tracks neuronal activity in the brain with respect to time. Clinical and research applications of MEG include the identification of regions affected by pathology as well as analysis of motor, cognitive, and behavioral brain processes. To further elucidate the relationship between neuronal activity and specific mental functions, MEG data will be collected in addition to the TMS data. This additional subset of data will be useful if TMS data collection does not provide statistically significant results.

Metabolomic Analyses:

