We will perform serum targeted analysis for LPC, autotaxin activity and LPA measurements pre and post-treatment. We will perform a highly specific mass spectrometry target analysis of LPC species from serum for clinical correlation. We will use authentic standards to accurately measure low and high levels of these biomarkers. This technique will be more reliable and reproducible for clinical applications. We will quantify autotaxin enzyme activity using a fluorometric assay to correlate with LPC measurements (Echelon Biosciences, K-4100). Samples will be collected in EDTA free tubes to avoid interference with analysis per manufacturer recommendations. We will quantify LPA using serum ELISA using the validated kit from Biosource (Reference MBS2024826). In the event that a significant change in autotaxin levels is not observed, we will evaluate untargeted global metabolomics profiling to identify possible disease biomarkers that are affected by NF1 and by treatment with NAC.

9. DATA ANALYSIS/METHODS:

Data Analysis and Data Monitoring-

Data will be maintained on the central servers of Neurology and Human Genetics at Cincinnati Children's Medical Center.

Statistical Analysis:

The purpose of this study is to generate preliminary estimates of effects NAC in NF1 on both behavior and potential biomarkers. Therefore we are not proposing a sample size calculation.

In general, our statistical analysis plan is based upon generalized linear models, particularly linear and logistic regression. The primary dependent variables for Aims 1 and 2 are continuous. For Aim 1, the primary behavioral outcome, which is also the primary outcome for the study, is the Dupaul ADHD rating scale score which rates ADHD behaviors, per the DSM5, in 18 domains, from 0 to 3, for a maximum of 54. Pre and post treatment ADHD will be evaluated with paired t test, with regression analysis to explore additional variables as per below. For Aim 2, PANESS scores and motor evoked potential amplitudes are the primary biomarker measures in the motor system. Analyses of these variables will also be performed pre- and post- treatment with paired t test. These variables will also be correlated, using Pearson or Spearman as appropriate, with the behavioral changes from Aim 1.

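### Untargeted metabolomics is made conditional on a non-significant autotaxin result in one section, although Aim 3 plans it without condition

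*Combined protocol and SAP*

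**What the plan says.** All references are to the combined protocol and SAP.

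- **Measurement of LPC-Autotaxin-LPA axis.** After describing the targeted serum assays (LPC species, autotaxin activity, LPA) before and after treatment, the section ends: "In the event that a significant change in autotaxin levels is not observed, we will evaluate untargeted global metabolomics profiling". The stated purpose of that step is to look for biomarkers influenced by the disease and by the drug.
- **Specific Aim 3.** The aim is "to evaluate metabolomics profiles as a possible disease biomarker that is affected by NF1 and by treatment with NAC as per Aim 1". No condition is attached. Hypothesis 4, under the same aim, expects certain profiles to predict clinical response.
- **Purpose of Study.** The third purpose is "to quantify metabolomics profiles at baseline and after treatment", again unconditional.
- **Metabolomics Data (background).** In the paragraph on untargeted profiling: "We plan to collect samples from NAC treated individuals to identify compounds that mark response to therapy".
- **Sampling.** The Phase I text draws blood for Aim 3 at study initiation. The Metabolomics row of Table 3 has four marks and no footnote or condition. The visit table before Study Procedures lists a metabolomics blood draw at Visits 1 and 3 and at Visits 2 and 4.
- **Metabolomic Analyses.** The feature-wide pipeline is set out with no trigger, and Bonferroni and FDR correction are named for the multiple testing.
- **Aim 2.2.** Autotaxin belongs to a different aim: "We propose to evaluate autotaxin as a candidate biomarker of oligodendrocyte dysfunction in NF1 participants".

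**The concern.** The same piece of work is a numbered aim in one place and a fallback for a different aim in another. An analyst following the axis section would stop at a significant autotaxin result and leave Aim 3 undone. An analyst following Aim 3 would run the profiling whatever autotaxin showed. Both would be following the protocol.

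The trigger is also undefined. The documents do not say which test, which contrast (before against after, or NAC against placebo) or which threshold makes an autotaxin change significant. The trigger refers to autotaxin levels, while the assay described measures enzyme activity. Whether Aim 3 is carried out could therefore be settled after the data are seen.

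At stake is the trial's stated product: preliminary biomarker findings to support a larger study. If untargeted profiles are analysed only when the targeted axis disappoints, the reported set of biomarkers is selected by result. The two approaches would also not be compared in the case where the axis responds.

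**Working it through.** The documents give no power, effect size or sequence-wide error figure for the biomarkers, so there is no stated number to reproduce. Two checks give the scale.

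**1. How strongly does Aim 3 depend on the autotaxin result?**

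Inputs:
- n = 20 children (Purpose of Study), taken as 20 complete pairs.
- α = 0.05 (Statistical Analysis). Sidedness is not stated; two-sided is assumed.
- Paired t test. The Statistical Analysis section names this for PANESS and motor evoked potentials but does not mention autotaxin, so it is an assumption here.
- Standardized autotaxin change d: not given, so a range is shown.

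Formula: the untargeted analysis is called for when the autotaxin test is not significant,

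P(trigger) = P(|T| < t₀.₉₇₅,₁₉), where T is noncentral t with 19 degrees of freedom and noncentrality d√20.

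| Assumed d | P(autotaxin significant) | P(trigger) |
|---|---|---|
| 0 | 0.050 | 0.950 |
| 0.2 | 0.136 | 0.864 |
| 0.3 | 0.247 | 0.753 |
| 0.5 | 0.565 | 0.435 |
| 0.8 | 0.924 | 0.076 |

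Under the axis section, the chance that Aim 3 is called for runs from 95% down to about 8% over this range. Under Aim 3 as written it is 100% throughout.

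**2. Does the trigger itself inflate false positives?**

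Assume that nothing truly changes, that the two steps are independent, and that each is held at 0.05 overall.

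- With the trigger: 0.05 + 0.95 × 0.05 = 0.0975.
- Both analyses always run: 1 − 0.95² = 0.0975.

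The two are identical, and remain so for any error rate a at the second step, because 0.05 + 0.95a = 1 − 0.95(1 − a). The condition affects what is analysed and reported. It does not raise the chance of at least one false positive.

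**The case against.** The best defence is that the axis section never says untargeted profiling will be done *only* after a null autotaxin result. With four other places planning metabolomics unconditionally and a full pipeline given with no trigger, the sentence could simply mark where attention turns if autotaxin is uninformative. That reading is possible, but the text does not state it, and the ordinary sense of the wording is conditional. The ambiguity is itself what needs removing.

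It is also fair to say that these biomarkers are labelled exploratory or experimental, and that the study is meant to yield preliminary estimates. That stands, and it limits the severity.

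Three stronger readings are tempting and are not supported:

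- **MEG as a second result-dependent fallback.** The TMS section says of MEG: "This additional subset of data will be useful if TMS data collection does not provide statistically significant results". But the preceding sentence collects MEG alongside TMS for a purpose that carries no condition; only its usefulness is tied to the TMS result. MEG relates to Aim 2.1, so it cannot contradict Aim 3. Its absence from the aims, the visit tables and the statistical section is a separate matter.
- **A flood of chance findings.** Multiplying the 5,206 compounds in the preliminary-data figure by its p<0.005 cut-off gives about 26 false leads (5,206 × 0.005 = 26.03). That figure's legend describes the 5,206 as already statistically significant, so it is not clearly the number tested. The cut-off belongs to preliminary work and was paired with a fold-change filter, and the trial's own univariate screen is to be corrected by Bonferroni and FDR. Any false leads would come from running the screen, which the fix does more often, not from the trigger.
- **Metabolomics data that would not exist.** Blood is drawn at all four visits regardless, and targeted LPC and LPA are measured regardless. Only the untargeted assay or its analysis is in question.

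**Conclusion.** The contradiction holds. On its natural reading, the axis section makes an exploratory aim depend on a non-significant result for another biomarker, while Aim 3, the study purpose and the sampling plan commit to metabolomics without condition. When autotaxin is significant, Aim 3 and Hypothesis 4 are left without an instruction to be analysed.

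For scale, the trigger fires about 95% of the time at d = 0, 44% at d = 0.5 and 8% at d = 0.8. These figures rest on 20 complete pairs, a two-sided paired t test at 0.05 and assumed values of d. A different contrast, or dropout, would shift them without changing the conclusion.

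The harm is selective conduct and reporting of an exploratory aim. No inflation of the two-step false-positive chance was found under the independence assumption. Severity is minor: no primary outcome, sample size or confirmatory claim depends on this sentence.

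**What to change.** Delete the conditional sentence at the end of Measurement of LPC-Autotaxin-LPA axis and replace it with wording along these lines: *Untargeted metabolomics profiling under Aim 3 will be run on the scheduled samples and reported whatever the autotaxin result. The autotaxin result will be reported whether or not it is significant. Both analyses are exploratory, and the feature-level multiplicity correction described under Metabolomic Analyses applies to the untargeted screen.*

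Once the trigger is gone, no decision hangs on the undefined autotaxin test, though naming its contrast in the Statistical Analysis section would still help the reader.

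The change is to wording only. It adds no visits or blood draws, since samples are already scheduled. The one real cost is the untargeted assays if the sponsor had hoped to skip them after a positive autotaxin result, although Aim 3 already commits to the profiling. The change does not lower the overall error rate across the two biomarker families, which is why the exploratory label matters.

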In order to better understand treatment mechanisms, and possibly predict long-term outcomes, we propose concurrently to explore Specific Aim 1 (1.1, 1.2, and 1.3) exploratory potential disease biomarkers as outlined below. The primary outcome of this study is motor function rated with the Physical and Neurological Examination for Subtle Signs (PANESS), a validated scale that consistently demonstrates significant impairments in children with ADHD, and which our preliminary data suggest may demonstrate more extreme problems in children with NF1. The first exploratory biomarker is motor system inhibitory physiology, measured using Transcranial Magnetic Stimulation (TMS). Preliminary measures in our NF1 population also show abnormalities similar to established findings in ADHD. The second exploratory biomarker is metabolomics profiling for the biomarker of oligodendrocyte dysfunction in NF1 participants: autotaxin. Preliminary data in our NF1 population showed specific signal abnormalities in the NF1 population compared to healthy controls. Therefore, we propose to perform a double-blind placebo controlled, prospective, Phase IIa study to explore safety, tolerability, and efficacy of NAC on learning and motor behavior in children with NF1 aged 8 through 16 years old.

PURPOSE OF STUDY:

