The study physician ([name], or qualified designee) is responsible for evaluating the participant's clinical state each month, including both the progress of treatment and the occurrence of adverse events/tolerability problems. The study physician will interview child and family regarding level of clinical improvement and tolerability. They may obtain the participant's weight, pulse and blood pressure. Concomitant medications and adverse effects (e.g. SERS) will be reviewed (in person or via phone or email). [name] or designee will also question the subjects as to compliance with study medication. If needed [name] or designee may ask for the participant to bring in medication bottles to check pill count and can also check to see if the prescription has been filled/refilled at the reported times. At a monthly medication visit, the study physician or designee will: 1) do vitals; 2) evaluate adverse events both spontaneous and elicited, 3) and fill out medication log/assess compliance. Per FDA *Guidance for Industry: Suicidal Ideation and Behavior: Prospective Assessment of Occurrence in Clinical Trials*, an assessment for suicide (Columbia Suicide Severity Rating Scale, C-SSRS) will be performed.

Version 9.0 MAR2020 Page **14** of **24**

End of Phase I and End of Study visits (Visit 2, 4).

Participant will undergo a TMS evaluation at completion of 8 weeks of NAC or placebo. An independent rater will assess clinical outcome with the primary outcome measure (PANESS scale), the same rater that performed the baseline neuropsychometrics assessment (whenever possible). Participants will also meet with [name] and [name] to conduct the study closeout visit which consists of 1) vitals; 2) evaluate adverse events both spontaneous and elicited, 3) fill out medication log/assess compliance, 4) assess collateral symptoms of depression/anxiety which may have developed during the trial, 5) evaluate parent ratings, 6) write a progress note documenting the visit, 7) assign motor/learning behavior improvement, 8) meet with participant and family to review the child's performance during the trial to present a set of clinical recommendations for future care (not restricted to medication, and not for a specific medication). Per FDA Guidance for Industry: Suicidal Ideation and Behavior: Prospective Assessment of Occurrence in Clinical Trials, an assessment for suicide (Columbia Suicide Severity Rating Scale, C-SSRS) will be performed.

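### The protocol names two different primary outcomes, PANESS and the DuPaul ADHD rating scale, and nothing says which governs

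*Combined protocol and SAP*

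**What the plan says.** The opening text, before the Purpose of Study heading, states: "The primary outcome of this study is motor function rated with the Physical and Neurological Examination for Subtle Signs (PANESS". The description of Visits 2 and 4 (End of Phase I and End of Study visits) agrees: "An independent rater will assess clinical outcome with the primary outcome measure (PANESS scale". The PANESS scale paragraph, under Study Procedures, also calls it the main battery of interest.

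Section 9, Statistical Analysis, says something different. For Aim 1, "the primary behavioral outcome, which is also the primary outcome for the study, is the Dupaul ADHD rating scale score". PANESS then appears in another role: "For Aim 2, PANESS scores and motor evoked potential amplitudes are the primary biomarker measures in the motor system". A pre/post paired t test is assigned to each scale. The same section sets alpha at 0.05 for hypothesis tests unless otherwise noted, and adds mixed models for change over time.

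The Specific Aims section has the heading "Specific Aim 1: Primary Outcome of Study". Two sub-aims stand under it. Aim 1.1 is "Characterize effects of NAC treatment on motor function in kids with NF1 using the Physical and Neurological Examination for Subtle Signs (PANESS", and Aim 1.2 is "Characterize effects of NAC treatment on ADHD symptoms in children with NF1", the latter rated with the DuPaul scale. Neither is ranked above the other.

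**The concern.** A trial's primary outcome should be identifiable from its protocol without judgement. Here two sections give the role to PANESS and the section that specifies the analysis gives it to the DuPaul score.

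The scales are not interchangeable. PANESS is a motor examination administered by a research assistant. The DuPaul scale is an 18-item parent form. They could well give different answers on NAC.

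If one scale shows an effect and the other does not, one part of the protocol supports reporting a positive primary finding and another part supports reporting that the primary outcome did not improve. Whoever writes the report could pick the section that suits the result. The Purpose of Study section intends these results to support funding for a larger trial, so the choice of headline has consequences.

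**Working it through.** **1. The sections side by side**

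| Place | Role of PANESS | Role of DuPaul ADHD score |
|---|---|---|
| Introduction | Primary outcome of the study | Not named |
| Specific Aims | Aim 1.1, under the primary-outcome heading | Aim 1.2, under the same heading |
| Visits 2 and 4 | Primary outcome measure | Not named |
| PANESS scale paragraph | Main battery of interest | Not named |
| Section 9, Statistical Analysis | Aim 2 biomarker | Primary outcome for the study |

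**2. Can the texts be reconciled?**

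- *Primary within a domain only.* Had section 9 called the DuPaul score only the primary behavioural outcome, it could coexist with PANESS as the study primary. The clause that follows makes it the primary outcome for the whole study, which closes that reading.
- *Co-primaries.* The Aim 1 heading is singular and covers both scales. No section declares two primaries or says what success would require. Section 9 takes PANESS out of Aim 1 altogether.
- *A slip in the aim number.* The Aim 2 label in section 9 conflicts with Aim 1.1, but it is not isolated. The neurobiology part of the Background and the TMS preliminary data also treat PANESS as an Aim 2 biomarker.

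No reading removes the conflict.

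**3. Size of the selection risk (illustrative)**

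The protocol gives no power, effect size, standard deviation or dropout rate, so there is no stated figure to reproduce. Inputs from the documents are alpha = 0.05 and n = 20. Assumptions are two-sided tests, one test per scale, and a correlation ρ between the two test statistics.

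For independent tests at 0.05 each, the chance of at least one false positive is 1 − (1 − 0.05)² = 1 − 0.9025 = 0.0975.

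For correlated tests it is 1 − P(|Z₁| < c and |Z₂| < c), with Z bivariate normal. Here c = 1.960 at 0.05 and c = 2.241 at 0.025. The chance that both reject is 2α minus that figure; at ρ = 0.5 and α = 0.05, 0.10 − 0.0907 = 0.0093.

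| ρ (assumed) | At least one, 0.05 each | At least one, 0.025 each | Both, 0.05 each |
|---|---|---|---|
| 0 | 0.0975 | 0.0494 | 0.0025 |
| 0.3 | 0.0951 | 0.0484 | 0.0049 |
| 0.5 | 0.0907 | 0.0465 | 0.0093 |
| 0.7 | 0.0835 | 0.0430 | 0.0165 |
| 0.9 | 0.0704 | 0.0362 | 0.0296 |

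Simulated one-sample t tests on change scores with n = 20 agree to within about 0.002 (0.098, 0.095, 0.091, 0.084 and 0.072 in the second column).

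The last column assumes no effect on either scale. If one scale has a real effect, the chance of falsely claiming both can approach 0.05 but cannot exceed it, which is why a both-must-succeed rule needs no split.

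**4. What each success rule would cost**

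The detectable standardised paired effect d at 80% power solves P(|T| > t₁₋α/₂, n−1) = 0.80, with T noncentral t on n − 1 degrees of freedom and noncentrality d√n.

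| Complete pairs | d at 0.05 | d at 0.025 |
|---|---|---|
| 20 (no dropout assumed) | 0.66 | 0.74 |
| 16 (20% loss assumed) | 0.75 | 0.84 |

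If both scales must succeed at 0.05 with true d = 0.66 on each and 20 pairs, simulated joint power is 0.64, 0.685 and 0.75 at ρ = 0, 0.5 and 0.9.

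**The case against.** The best defence is that this is a pilot. Section 9 says "The purpose of this study is to generate preliminary estimates of effects NAC in NF1 on both behavior and potential biomarkers" and declines a sample size calculation. There is no go/no-go criterion, so calling the trial positive or negative imports a confirmatory verdict that the protocol never sets up, and splitting alpha in a study of 20 children may be excessive.

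Part of this stands. No stated power or sample size is invalidated, and alpha splitting is needed only if the sponsor wants success on either scale to count. But the Specific Aims state directional hypotheses for both scales, and section 9 plans tests of both at 0.05. Even a pilot that only estimates effects must say which estimate is primary.

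The figures are also open to challenge. The correlations are assumed, sidedness is not stated in the protocol, and no section states an either-scale rule. The pre/post wording does not say which crossover visits form the pair, so the standardised effects are generic. This is fair. The figures indicate scale only, and the finding rests on the text.

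**Conclusion.** The concern holds and must be fixed. Version 9.0 contradicts itself on the primary outcome: two sections name PANESS, the statistical section names the DuPaul score, and the Specific Aims do not settle it. The front matter removed before review was not seen, so this conclusion covers the visible text.

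The harm is an undefined primary result and room for selective reporting. Under the stated assumptions, freedom to claim either scale raises the nominal 5% error to between 7.0% and 9.8%. The textual conflict does not depend on those assumptions. The documents do not show which scale was intended, so the sponsor has to decide.

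**What to change.** Before unblinding, the sponsor should do one of the following.

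1. Name one primary outcome, tested at 0.05, and label the other secondary.
2. Declare both primary and state the success rule: 0.025 each (or an equivalent family-wise procedure) if either suffices, or 0.05 each if both must succeed.

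Then align the introduction, the Specific Aims, the Visit 2 and 4 description, the PANESS scale paragraph and section 9. State whether PANESS belongs to Aim 1 or Aim 2, and bring the Background and TMS preliminary data text into line. The Emergency Study Extension says that all active participants are already in phase II, between weeks 14 and 18. The change should therefore carry a dated record that it was made without access to outcomes by treatment arm.

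Option 1 costs wording, and one scale loses primary status. Option 2 with an either-scale rule raises the detectable effect from about 0.66 to 0.74 with 20 pairs. Option 2 with a both-scales rule keeps 0.05 for each test but lowers the chance of overall success to about 64% to 75% in the case worked above.
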